10.3.6.1 Complete neurological examination

The complete neurological examination will include selected assessments of mental status, cranial nerves, sensory systems, motor functions, reflexes, and coordination/cerebellar function.

10.3.6.2 Brief neurological examination

The brief neurological examination will include selected assessments of general neurological status, reflexes, muscle strength, and coordination/cerebellar function.

10.3.7 Assessment of suicidality

Suicidality will be assessed by trained study personnel using the C-SSRS (Columbia University Medical Center, 2012). This scale will be used for screening as well as to assess suicidal ideation and behavior that may occur during the study. The C-SSRS will be completed according to the schedule of study assessments in Table 5-1, Table 5-2, and Table 5-3.

All subjects who are ≥ 6 years of age will complete the "Baseline/Screening" version of the C-SSRS at Visit 1 and will complete the "Since Last Visit" version at subsequent visits. If a subject becomes 6 years of age during the study, the "Already Enrolled" version of the C-SSRS should be used at the first visit at which the subject is 6 years of age, and the "Since Last Visit" version should be used at subsequent visits.

The C-SSRS is not validated for subjects < 6 years of age and will not be used for this population. Subjects should be monitored for any changes in mood, ideas, or behavior for warning signs of depression. The investigator should be aware of common warning signs that might be a signal for risk of depression. For common signs and symptoms of depression in children younger than

6 years old, reference should be made to the current version of the Diagnostic and Statistical Manual of Mental Disorders published by the American Psychiatric Association. Each subject's parent(s)/legal representative(s)/caregiver(s) (in accordance with local regulation) should also be advised accordingly and effort should be made at clinic visits to specifically assess potential depression.

10.3.8 Achenbach CBCL

The Achenbach CBCL is a widely used validated questionnaire to evaluate a child's competencies and behavioral/emotional problems. Behavioral problems will be scored by the parent(s)/legal representative(s).

The Achenbach CBCL/1½ -5 is for children <5 years and 11 months of age, and the CBCL/6-18 is for children ≥6 years to <18 years of age; the questionnaire is to be completed by the parent(s)/legal representative(s). For each subject, the same version of the scale that is completed at Visit 2 should be maintained for the duration of the study in accordance with the tabular schedules of study procedures (Table 5-1) and should be completed by the same parent/legal representative. The completion of the Achenbach CBCL will require approximately 45 minutes.

In both questionnaires, the occurrence of certain problems and behaviors in the past 6 months will be scored on the following scale:

- 0=not true (as far as known)
- 1=somewhat or sometimes true
- 2=very true or often true

Eight syndrome scores will be calculated from these questionnaires, which will in turn be summarized by 2 composite scores. Additionally, for each score on the questionnaire, syndrome, and total level, categorizations based on a normative sample will be used to evaluate normal, borderline, or clinically relevant behavior.

In addition, the Achenbach CBCL/6-18 includes ratings related to performance in school, activities in leisure time, and special interests.

10.3.9 BRIEF

The BRIEF-P and the BRIEF are validated tools that will be used for the evaluation of subjects ≥2 years to <5 years of age and ≥5 years of age, respectively. The BRIEF-P and BRIEF will be used only in countries where a translated scale is available. For each subject, the same version (BRIEF-P or BRIEF) that is used at Visit 2 should be maintained for the duration of the study in accordance with the tabular schedules of study procedures (Table 5-1).

The BRIEF-P and BRIEF include rating forms used by parents to assess subjects' executive functioning. Executive functions broadly encompass a set of cognitive skills that are responsible for the planning, initiation, sequencing, and monitoring of complex goal-directed behavior.

The BRIEF-P rating form consists of items that measure various aspects of executive functioning: Inhibit, Shift, Emotional Control, Working Memory, and Plan/Organize. The clinical scales form 3 broad indexes (Inhibitory Self-Control, Flexibility, and Emergent Metacognition) and 1 composite score (Global Executive Composite).

The BRIEF rating form contains items in nonoverlapping clinical scales. These theoretically and statistically derived scales form 2 broader Indexes: Behavioral Regulation (3 scales) and Metacognition (5 scales), as well as a Global Executive Composite score.

Both the BRIEF-P and the BRIEF include validity scales to measure negativity and inconsistency of responses.

11 ASSESSMENT OF PHARMACOKINETICS

Blood samples for analysis of LCM plasma concentrations will be collected at any time between 2 successive bid doses, according to the schedule of study assessments in Table 5–1. The time the subject took the most recent dose of IMP and the time of blood sampling must be recorded. Actual dosing and sampling times will be recorded in the eCRF to the minute.

The central laboratory will store the plasma samples at -20°C until analysis. Blood draws for these assessments will coincide with the blood collection times for assessment of the hematology and clinical chemistry parameters. Time and date of each blood draw will be documented on the eCRF.

Instructions on blood sample collection, processing, storage, and labeling/shipping are provided in the laboratory manual for this study.

12 STUDY MANAGEMENT AND ADMINISTRATION

12.1 Adherence to protocol

The investigator should not deviate from the protocol. In medical emergencies, the investigator may use his/her medical judgment and may remove a study participant from immediate hazard before notifying UCB (or its representative) and the IRB/IEC in writing regarding the type of emergency and the course of action taken.

12.2 Monitoring

UCB (or designee) will monitor the study to meet the sponsor's monitoring SOPs, ICH-GCP guideline, and applicable regulatory requirements, and to ensure that study initiation, conduct, and closure are adequate. Monitoring of the study may be delegated by UCB to a CRO or a contract monitor.

The investigator and his/her staff are expected to cooperate with UCB (or designee) and to be available during the monitoring visits to answer questions sufficiently and to provide any missing information. The investigator(s)/institution(s) will permit direct access to source data/documents for study-related monitoring, audits, IRB/IEC review, and regulatory inspection(s).

The investigator will allow UCB (or designee) to periodically review all eCRFs and corresponding source documents (eg, hospital and laboratory records for each study participant). Monitoring visits will provide UCB (or designee) with the opportunity to evaluate the progress of the study, verify the accuracy and completeness of eCRFs, ensure that all protocol requirements, applicable authorities regulations and investigator's obligations are being fulfilled, and resolve any inconsistencies in the study records.

12.2.1 Definition of source data

All source documents must be accurate, clear, unambiguous, permanent, and capable of being audited. They should be made using some permanent form of recording (ink, typing, printing,

optical disc). They should not be obscured by correction fluid or have temporary attachments (such as removable self-stick notes). Printouts of eCRF screens are not considered acceptable source documents.

Source documents are original records in which raw data are first recorded. These may include hospital/clinic/general practitioner records, charts, diaries, x-rays, laboratory results, printouts, pharmacy records, care records, ECG or other printouts, completed scales, or quality of life questionnaires, for example. Source documents should be kept in a secure, limited access area.

If the source documents are maintained by the investigator in a computerized system, the monitor should ensure that electronic records are ALCOA (attributable, legible, contemporaneous, original, and accurate) compliant and that there is proper access control, validation, and audit trail available upon request. If the monitor has no direct access to the original electronic medical records, the certified copies should be generated by the investigator and used for the study purposes. Accuracy and completeness of data on the certified copies should be verified by the monitor to maintain ongoing compliance.

12.2.2 Source data verification

Source data verification ensures accuracy and credibility of the data obtained. During monitoring visits, reported data are reviewed with regard to being accurate, complete, and verifiable from source documents (eg, subject files, recordings from automated instruments, tracings [ECG], x-ray films, laboratory notes). All data reported on the eCRF should be supported by source documents, unless otherwise specified in Section 12.2.1.

12.3 Data handling

12.3.1 Case report form completion

The investigator is responsible for prompt reporting of accurate, complete, and legible data in the eCRFs and in all required reports.

Any change or correction to the eCRF after saving must be accompanied by a reason for the change.

Corrections made after the investigator's review and approval (by means of a password/electronic signature) will be reapproved by the investigator.

The investigator should maintain a list of personnel authorized to enter data into the eCRF.

Detailed instructions will be provided in the eCRF completion guidelines.

12.3.2 Database entry and reconciliation

Case Report forms/external electronic data will be entered/loaded into a validated electronic database using a Clinical Data Management System (CDMS). Computerized data cleaning checks will be used in addition to manual review to check for discrepancies and to ensure consistency of the data. This study is performed using electronic data capture (EDC); the data are entered into the eCRFs once and are subsequently verified.

An electronic audit trail system will be maintained within the CDMS to track all data changes in the database once the data have been saved initially into the system or electronically loaded. Regular backups of the electronic data will be performed.

12.3.3 Subject Screening and Enrollment log/Subject Identification Code list

The subject's screening and enrollment will be recorded in the Subject Screening and Enrollment Log.

The investigator will keep a Subject Identification Code list. This list remains with the investigator and is used for unambiguous identification of each subject.

The subject's consent/assent and enrollment in the study must be recorded in the subject's medical record. These data should identify the study and document the dates of the subject's participation.

12.4 Termination of the study

UCB reserves the right to temporarily suspend or prematurely discontinue this study either at a single site, multiple sites, or at all sites at any time for reasons including, but not limited to, safety or ethical issues, inaccurate or incomplete data recording, noncompliance, or unsatisfactory enrollment with respect to quality or quantity.

If the study is prematurely terminated or suspended, UCB (or its representative) will inform the investigators/institutions and the regulatory authority(ies) of the termination or suspension and the reason(s) for the termination or suspension, in accordance with applicable regulatory requirement(s). The IRB/IEC should also be informed and provided with reason(s) for the termination or suspension by the sponsor or by the investigator/institution, as specified by the applicable regulatory requirement(s). In addition, arrangements will be made for the return of all unused IMP and other material in accordance with UCB procedures for the study.

12.5 Archiving and data retention

The investigator will maintain adequate records for the study including eCRFs, medical records, laboratory results, Informed Consent/Assent documents, drug dispensing and disposition records, safety reports, information regarding participants who discontinued, and other pertinent data.

All essential documents are to be retained by the investigator until at least 2 years after the last approval of a marketing application in an ICH region and until there are no pending or contemplated marketing applications in an ICH region, or at least 2 years have elapsed since the formal discontinuation of clinical development of the IMP. These documents should be retained for a longer period, however, if required by the applicable regulatory requirement(s) or by an agreement with UCB (CPMP/ICH/135/95, 2002 [Section 4.9.5]). The investigator will contact UCB for authorization prior to the destruction of any study records or in the event of accidental loss or destruction of any study records. The investigator will also notify UCB should he/she relocate or move the study-related files to a location other than that specified in the sponsor's trial master file.

12.6 Audit and inspection

The investigator will permit study-related audits mandated by UCB, after reasonable notice, and inspections by domestic or foreign regulatory authorities.

The main purposes of an audit or inspection are to confirm that the rights and well-being of the subjects enrolled have been protected, that enrolled subjects (ie, signing Informed Consent/Assent and undergoing study procedures) are appropriate for the study, and that all data relevant for the evaluation of the IMP have been processed and reported in compliance with the planned

arrangements, the protocol, investigational site, and IRB/IEC SOPs, ICH/GCP, and applicable regulatory requirements.

The investigator will provide direct access to all study documents, source records, and source data. If an inspection by a regulatory authority is announced, the investigator will immediately inform UCB (or designee).

12.7 Good Clinical Practice

Noncompliance with the protocol, ICH/GCP, or local regulatory requirements by the investigator, institution, institution staff, or designees of the sponsor will lead to prompt action by UCB to secure compliance. Continued noncompliance may result in the termination of the site's involvement in the study.

13 STATISTICS

A description of statistical methods follows and will be described in more detail in the Statistical Analysis Plan (SAP).

13.1 Definition of analysis sets

13.1.1 Screened Set

The Screened Set consists of all subjects who have entered screening at Visit 1, have a signed Informed Consent/Assent form, and have at least basic demographic data available.

13.1.2 Randomized Set

The Randomized Set (RS) is a subset of the Screened Set and consists of all subjects who were randomized at the Randomization Visit (Visit 2).

13.1.3 Safety Set

The Safety Set (SS) is a subset of the RS and consists of all subjects who have been treated with at least 1 dose of study drug, either LCM or placebo. This population will serve as the primary population for assessing safety endpoints.

13.1.4 Full Analysis Set

The Full Analysis Set (FAS) is a subset of the SS consisting of all subjects with at least 1 seizure diary assessment during the Treatment Period. This population will serve as the primary population for assessing efficacy endpoints.

13.1.5 Per Protocol Set

The Per Protocol Set (PPS) is a subset of the FAS excluding subjects who completed fewer than 6 weeks of treatment or subjects with important protocol violations affecting the interpretation of the primary efficacy analysis. Important protocol violations will be determined prior to unblinding.

13.2 General statistical considerations

Descriptive statistics will be used to provide an overview of the primary, secondary, and other variable results. For categorical parameters, the number and percentage of subjects in each category will be presented. The denominator for percentages will be based on the number of subjects appropriate for the purpose of analysis. For continuous parameters, descriptive statistics will include number of subjects, mean, standard deviation, median, minimum, and maximum.

13.3 Planned efficacy analyses

13.3.1 Analysis of the primary efficacy variable

The primary efficacy variable, time to second PGTC seizure during the 24-week Treatment Period, will be evaluated using a Cox proportional hazards regression model (Cox, 1972), with an effect for treatment, stratifying for the subjects' Baseline PGTC seizure frequency (≤ 2 per 28 days vs > 2 per 28 days in the 16 weeks prior to randomization) and age at informed consent (≥ 4 to < 12 years of age, ≥ 12 to < 18 years of age vs ≥ 18 years of age). Pooling strategies for strata with a low number of events will be defined in the SAP prior to unblinding. Subjects who prematurely discontinue from the study will be censored on the date of last dose of study drug during the Treatment Period.

Additionally, a Kaplan-Meier (KM) plot for time to second PGTC seizure as well as the KM estimate for the median time to second PGTC seizure will be provided. This analysis will be performed using the FAS population.

Testing for the primary endpoint will be done at the 5% level (2-sided). A gatekeeping strategy (Marcus et al, 1996) will be used to test the key secondary efficacy variable provided that the primary endpoint is statistically significant (See Section 13.3.2 for additional details). No additional adjustments for multiplicity are required as all additional inferences will be hypothesis-generating only.

The following additional sensitivity analyses on the primary efficacy endpoint will be conducted in order to assess the effect of dropouts, protocol deviations, and operational bias on the primary endpoint:

- Repeat the primary analysis using the PPS.
- Repeat the primary analysis using the FAS, except all subjects who prematurely discontinue due to lack of efficacy, consent withdrawn, or lost to follow-up will be analyzed as treatment failures (ie, events at the time of discontinuation).
- Repeat the primary analysis using the FAS, except all subjects who prematurely discontinue due to lack of efficacy or AEs only will be analyzed as treatment failures.
- Repeat the primary analysis using the FAS, comparing the event rates at each interim analysis to examine possible operational bias due to unblinding.

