At Visit 1, subjects and/or caregivers will be given a seizure diary to document all types of seizures, concomitant AEDs, and any other pertinent health status information. Seizure frequency and type eligibility will be verified by reliably documented seizure history collected (eg, in a seizure diary) 12 weeks prior to Visit 1. In addition, prior to Visit 1, subjects are required to have had an EEG showing discharges consistent with IGE (eg, generalized ≥ 3 Hz epileptiform discharges and a normal EEG background). A confirmatory EEG may be performed during the Prospective Baseline, if approved by the Central Reviewer. Investigators will send a copy of the EEG report to the Central Reviewer. The report should include a detailed description of the background activity and abnormalities in the EEG as well as a clinical interpretation. The information provided will be reviewed and any questions regarding the subject's eligibility will be discussed with the investigator prior to the subject being randomized.

The Prospective Baseline begins with subject screening at Visit 1 (Week -4) and will last 4 weeks. Visit 1 will be conducted to evaluate subject eligibility for enrollment into the study. It is acceptable for this visit to be conducted on more than 1 day; although, it should not extend over a period longer than 7 consecutive days. Seizure count eligibility will be verified by data collected in a study seizure diary during the 4-week Prospective Baseline. Subjects and/or

caregivers will be contacted via telephone 2 weeks following Visit 1 to assess continued eligibility and will be reminded of the importance of accurate seizure diary completion. At Visit 2, subjects who complete the Prospective Baseline and meet all entry criteria except the minimum PGTC seizure criteria required for randomization (Baseline failures) may choose to enter EP0012. In this case, at the end of the Prospective Baseline, Visit 1 of EP0012 will be performed.

At the end of the Prospective Baseline (Visit 2), eligible subjects will be randomized to receive LCM or placebo (see [Table 7-1](#)) in a 1:1 fashion (active:placebo) and stratified by Baseline PGTC seizure frequency (≤ 2 per 28 days vs > 2 per 28 days for the 16-week Combined Baseline Period prior to randomization) and by age at informed consent (≥ 4 to < 12 years of age, ≥ 12 to < 18 years of age, and ≥ 18 years of age). The Treatment Period starts at the time of the Randomization Visit (Visit 2).

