6 SELECTION AND WITHDRAWAL OF SUBJECTS

6.1 Inclusion criteria

To be eligible to participate in this study, all of the following criteria must be met:

1. An Institutional Review Board (IRB)/Independent Ethics Committee (IEC) approved written Informed Consent/Assent form is signed and dated by the subject or by the parent(s) or legal representative. The Informed Consent form or a specific Assent form, where required, will be signed and dated by minors.
2. Subject/legal representative is considered reliable and capable of adhering to the protocol (eg, able to understand and complete diaries), visit schedule, and medication intake according to the judgment of the investigator.
3. Male and female subjects ≥ 4 years of age.
4. Subject with a confirmed diagnosis at least 24 weeks prior to Visit 1 and a disease onset prior to 30 years of age, consistent with IGE experiencing PGTC seizures (Type IIE) that are classifiable according to the ILAE Classification of Epileptic Seizures (ILAE, 1981).
5. Subject has ≥ 3 PGTC seizures during the 16-week Combined Baseline (12-week Historical Baseline plus 4-week Prospective Baseline) distributed as described below:
 - at least 3 PGTC seizures should have occurred during the 16-week Combined Baseline Period,

- at least 2 PGTC seizures should have occurred during the 12-week Historical Baseline Period,
- of the above seizures, at least 1 PGTC seizure should have occurred during the first 8 weeks and at least 1 PGTC seizure should have occurred during the second 8 weeks of the 16-week Combined Baseline Period.

The schematic diagram for the Combined Baseline Period eligibility is provided in [Figure 5-1](#). Examples of PGTC seizure frequency and eligibility are provided in the table below:

| Number of PGTC seizures | | | Is subject eligible? (In terms of Inclusion Criterion 5) |
|--|---------------------------------------|---|--|
| Historical Baseline Weeks -16 to -8 | Historical Baseline Weeks -8 to -4 | Prospective Baseline Weeks -4 to 0 (Visit 1 to Visit 2) | |
| 2 | 1 | 0 | Yes |
| 3 | 0 | 0 | No* |
| 1 | 1 | 1 | Yes |
| 0 | 2 | 1 | No |
| 1 | 2 | 0 | Yes |
| 2 | 0 | 1 | Yes |
| 1 | 0 | 2 | No |
| 1 | | 0 | No* |

Screening Visit

*Eligible to roll over to EP0012 if all other inclusion criteria are also met.

PGTC=primary generalized tonic-clonic

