13.8 Determination of sample size

Observing 125 events (subjects who had a second PGTC seizure during the 24-week Treatment Period) will provide 90% power to observe a hazard ratio of 0.56 at the 2-sided 5% level, assuming a dropout rate of 15%. The observed hazard ratio was based on a 25.4% survival rate for placebo and 48.2% for lamotrigine from a previous study comparing lamotrigine and placebo (French et al, 2007). The observed hazard ratio in the lamotrigine study was 0.533; however, in order to account for the possibility of an increased placebo response, as has been documented in recent clinical studies of AEDs, the hazard ratio was increased by 5% to 0.56 for estimating a sample size for this study. The rationale for the increase in the hazard ratio included the following considerations: different active compounds (LCM and lamotrigine) and a choice of time to second seizure as the primary efficacy endpoint (in the lamotrigine study, percent change in PGTC seizure frequency was the primary endpoint) (see rationale for second PGTC seizure in Section 5.4.2).

This is an event-driven study. Enrollment in the study will continue up to 125 events occurring or a maximum of 250 subjects randomized, whichever comes first.

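### The primary Cox model is valid but uses baseline seizure frequency only as a two-level stratum; pre-specifying the recorded 16-week count as a covariate would buy a modest, assumption-dependent gain in power at almost no cost.

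*Protocol*

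**What the plan says.** Section 13.3.1 fixes the primary model: time to second PGTC seizure "will be evaluated using a Cox proportional hazards regression model (Cox, 1972), with an effect for treatment, stratifying for the" two-level baseline PGTC frequency and age at consent. Treatment is the only regression term. On this model, only the pooling of strata with few events is expressly left to the SAP. None of the four sensitivity analyses listed there uses a numeric baseline frequency. Sections 13.3.2.1 and 13.3.2.2 analyse the key secondary variable and time to first seizure in the same manner, so the choice carries over to them.

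The model follows the randomisation, which is "in a 1:1 fashion (active:placebo) and stratified by Baseline PGTC seizure frequency" and age (Section 5.1).

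The exact count is available. Section 6.1, criterion 5, requires that "at least 3 PGTC seizures should have occurred during the 16-week Combined Baseline Period", which cannot be verified without counting. Section 5.1 obtains the count from 12 weeks of documented history plus a 4-week study diary. Section 4.1.3 needs each subject's numeric Combined Baseline frequency for the percent-change variables.

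Section 13.8 gives the sizing. The target is 125 second PGTC seizures, and the claim made for that target is that it "will provide 90% power to observe a hazard ratio of 0.56 at the 2-sided 5% level, assuming a dropout rate of 15" percent. Section 13.3.1 sets the level: "Testing for the primary endpoint will be done at the 5% level (2-sided").

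**The concern.** The endpoint is a second seizure of the type counted at baseline, so baseline frequency is the natural predictor. The protocol accepts this by stratifying on it. A two-level cut removes only part of the between-subject variation. What remains inside each stratum pulls the estimated hazard ratio towards 1 and weakens the test.

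The lost precision cannot be recovered later. Subjects exit once the 125th event occurs, and randomisation has "a maximum of 250 subjects randomized, whichever comes first". A better-used baseline value is the only extra information available from the same events, and it is already in the database.

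**Working it through.** **1. The plan's own figure.** Inputs from Section 13.8: hazard ratio (HR) 0.56, two-sided 5%, 90% power, 1:1.
- Events (Schoenfeld) = 4 × (1.960 + 1.282)² / (ln 0.56)² = 125.02.
- Power at 125 events = Φ(|ln 0.56| × √125 / 2 − 1.960) = 90.0%.
- Source HR = ln(0.482) / ln(0.254) = 0.533, and 0.533 × 1.05 = 0.56, as stated: "the hazard ratio was increased by 5% to 0.56 for estimating a sample size for this study".

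The sizing is arithmetically correct.

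**2. What the cut pools.** 2 per 28 days × 112/28 = 8 seizures in 16 weeks. The entry minimum of 3 is 3 × 28/112 = 0.75 per 28 days. The lower stratum covers 3 to 8 seizures, a ratio of 8/3 = 2.7. The upper stratum covers 9 or more, without limit.

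**3. Gain from adding log(count).** The protocol gives neither a distribution of counts nor a prognostic slope, so everything in this step rests on assumptions.

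*Proportional-hazards simulation.* HR 0.56 conditional on the count, 225 subjects, 125 events, 800 trials per setting. Strata were two frequency levels by two pooled age levels (assumed). The slope is the log-hazard increase per unit of log count.

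| Slope | Share above cut | Power, strata only | Power, with log count |
|---|---|---|---|
| 0 | 14% | 89.2% | 89.1% |
| 0 | 32% | 90.4% | 90.2% |
| 0.5 | 14% | 89.0% | 90.0% |
| 0.5 | 32% | 91.5% | 92.1% |
| 1.0 | 14% | 85.3% | 87.6% |
| 1.0 | 32% | 84.0% | 87.3% |
| 1.5 | 14% | 83.3% | 88.5% |
| 1.5 | 32% | 83.1% | 90.6% |

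At slopes 1.0 to 1.5 the strata-only HR moves from 0.56 to about 0.58–0.59. Each power figure carries a Monte Carlo error of about 1 point.

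*Lognormal seizure-rate simulation.* Rates conditioned on criterion 5 (median 1 per 28 days, log-SD 0.6 or 0.9), within-subject drift, a 40% placebo fall, 15% dropout, 164 to 168 subjects, about 125 events, 1,500 trials per setting. Power rose from 91.3 to 92.7%, 93.5 to 95.3% and 95.9 to 97.6%. The squared test statistic rose by 6% to 16%, equivalent to about 8 to 20 extra events (0.06 × 125 = 7.5; 0.16 × 125 = 20). A second batch of this kind (126 to 134 events, 2,500 trials per setting) gave 90.6 to 91.6%, 94.2 to 96.4% and 94.7 to 97.4%.

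*Gamma-Poisson simulation.* 400 trials per setting, fitted slopes 0.9 to 1.4. Gains ran from about 1 to 11 points, for example 82.3 to 87.0% and 78.5 to 87.7%, and were about 1 point where subjects differed little.

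**4. Type I error.** With 3,500 null trials per setting, two-sided rejection was 5.5% and 5.2% with the covariate, against 5.1% and 5.2% without. In 1,500 null trials, one-sided rejection was 3.0% with and 2.6% without. The standard error is about 0.4 points in each case, so there is no clear inflation, though a very small one cannot be excluded.

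**The case against.** Analysing by the randomisation strata is standard, and the stated power is right. In the lognormal simulations the strata-only model exceeds 90% power in every setting. All of this stands, and it is why the point is about efficiency.

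A reader might infer from the 83–85% rows that the trial is underpowered as planned. The documents do not support that. Those rows treat 0.56 as conditional on the count, whereas Section 13.8 derives its planning value from overall survival proportions of 25.4% and 48.2%. A hazard ratio on that scale may already contain the dilution from differences between subjects, so subtracting it again would count it twice.

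A reader might also infer that slow recruitment makes the gain pressing. The rationale for Protocol Amendment 5 describes recruitment as extremely challenging only for paediatric subjects.

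The lognormal setting also departs from the plan. About 125 events from 164 to 168 subjects is a rate near 75%. The protocol's survival figures imply (0.746 + 0.518)/2 = 63%, or about 125/0.632 = 198 subjects before dropout. This limits how literally its gains can be taken.

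The covariate has costs. It assumes a log-linear effect. Twelve of the 16 weeks are pre-study history, so the count is imperfectly measured and may regress to the mean after selection on a minimum of 3. The reported hazard ratio also becomes conditional on the count and typically lies slightly further from 1. These are reasons to show both models. They do not justify leaving the count out, because the strata are kept and the loss is only about 0.1 to 0.2 points if the count carries no information.

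Finally, an adjusted supportive analysis could sit in an SAP not seen here. That would not alter the primary model, which the protocol itself fixes.

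**Conclusion.** The point holds as an efficiency weakness in a valid analysis. The model discards a recorded baseline value that probably predicts the endpoint.

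The direction is firm; the size is not. It depends on how widely baseline counts vary within strata and how strongly they predict the second seizure, neither of which the protocol states. The reasonable range is about no gain if the count is not prognostic within strata, about 1 to 3 points of power in plausible settings, and more (5 to 8 points at slope 1.5, up to about 11 in the Gamma-Poisson settings) if the association is strong. Nothing here shows that the planned test is biased, that its Type I error is wrong or that 125 events are too few.

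**What to change.** Before unblinding, amend Section 13.3.1 and the SAP as follows:

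- Keep the randomisation strata, with whatever pooling rule the SAP sets.
- Add log(Combined Baseline PGTC seizures per 28 days) as one pre-specified continuous covariate in the primary Cox model. Every subject meeting criterion 5 has a count of at least 3, so the logarithm is defined.
- Use the same model for time to first PGTC seizure.
- Report the strata-only model as a sensitivity analysis.
- State that the primary hazard ratio is conditional on the baseline count and that the count's effect is assumed log-linear.

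The cost is a line or two of wording. It needs no new data and no change to trial conduct, event target or sample size. The change must be made while treatment codes are still blinded; after that, the adjusted model could only be supportive.
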